The CAB population PK model has been updated with PK data from ÉCLAIR (an additional 94 males) and LATTE-2 (an additional 230 participants; 216 males and 14 females), significantly increasing the data in the population PK dataset. The absorption rate constant for the entire population following CAB LA for the new model was increased approximately 2-fold ($4.54 \times 10^{-4} \text{ hr}^{-1}$ to $9.19 \times 10^{-4} \text{ hr}^{-1}$; i.e., more rapid absorption) as compared to the previous model and resulted in higher peak to trough ratios than previously observed. Sex remains a significant covariate in the model affecting the absorption rate constant following LA administration (KA LA), reflecting slower absorption in females than in males. Additional data from HPTN077 will increase the data obtained from females in the model to improve understanding of the impact of sex on KA LA.

Simulations based on the updated population PK model have been conducted to evaluate several potential dosing regimens. Currently, the HPTN077 Cohort 2 regimen (CAB LA 600 mg IM at two time points 4 weeks apart and every 8 weeks (Q8W) thereafter) is planned for evaluation in long-term Phase 3 PrEP studies. CAB LA 600 mg IM is the largest CAB LA dose that can be administered by single injection (3mL of 200 mg/mL nanosuspension). For these reasons, a single 600 mg IM is the proposed dose for evaluation of plasma and tissue PK in this study. Simulated profiles following a single CAB LA 600 mg IM injection one week after discontinuation of the CAB 30 mg once daily oral lead-in to evaluate safety are shown for males and females separately (Figure 2, Figure 3). The profiles show the last oral dose, which are expected to achieve mean peak and trough concentrations of 7.5 $\mu\text{g/mL}$ and 4.2 $\mu\text{g/mL}$, respectively. Consistent with the impact of sex on absorption, males will achieve a higher C_{max} of ~3 $\mu\text{g/mL}$ than females, who will achieve a C_{max} of ~1.35 $\mu\text{g/mL}$. Plasma concentrations are expected to remain above 4x PA-IC₉₀ (0.664 $\mu\text{g/mL}$) for approximately 4 weeks and above PA-IC₉₀ (0.166 $\mu\text{g/mL}$) for approximately 8 weeks in 95% of males; greater variability in concentrations between 8 and 12 weeks post injection is expected in males. Plasma concentrations are expected to remain above the PA-IC₉₀ (0.166 $\mu\text{g/mL}$) in 95% of females throughout the 12-week tissue sampling period.

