Cervical and vaginal biopsy via speculum exam	It is possible that the participant may experience mild discomfort, embarrassment, or, rarely, pain during speculum exam and biopsies. There is also a small risk of bleeding and an extremely low risk of infection after biopsy. In rare circumstances, the bleeding may require blood transfusions and surgical repair. A small amount of discomfort during sexual intercourse may follow in the few days after the procedure.	If there is an adverse event, participants will be referred immediately to the appropriate care. If there is any pain experienced during the procedures, the study clinician will adapt or stop the procedures. Subjects should abstain from inserting anything into the vagina (e.g., tampons, sexual intercourse) within 72 hours after cervical or vaginal biopsies.
Colonic biopsies via flexible sigmoidoscopy	Flexible sigmoidoscopy is a commonly practiced medical procedure and the endoscopic procedures done in this trial will not involve any unusual risks or discomforts. The risks associated with these procedures include mild discomfort and the feeling of having a "bloated stomach". Endoscopic biopsies are painless and heal quickly within 3 days. On extremely rare occasions, the endoscopic procedure or biopsies may lead to pain, infection (sepsis), bleeding or perforation of the gastrointestinal tract. Perforation occurs approximately once out of every 10,000 procedures. If this extremely rare complication occurs, antibiotics and surgery to repair the tear may be necessary. In rare circumstances, the bleeding may require blood transfusions and surgical repair. Subjects will self-administer a 125 mL enema several hours prior to the flexible sigmoidoscopy procedure. The main risk from having an enema is temporary discomfort. Some air may be pumped into the rectum as well, causing a bloating or gassy sensation. Very rarely, the enema tip may cause a perforation, as described above. Subjects will also be asked to have nothing to eat for 8 hours prior to the endoscopy procedure.	This procedure will be performed exclusively by experienced practitioners of endoscopy, who are familiar with safety procedures and mitigation of any complications that should ensue.

Potential Risk of Clinical Significance	Summary of Data/Rationale for Risk	Mitigation Strategy

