9.4. Key Elements of Analysis Plan

Pharmacokinetic analysis will be the responsibility of the Clinical Pharmacokinetics Modeling & Simulation Department within GSK. All PK data will be stored in the Archives, GSK Pharmaceuticals, R&D.

Statistical analyses of the PK parameter data will be the responsibility of Clinical Statistics, GSK.

Data will be listed and summarized according to GSK reporting standards, where applicable. Listings will be sorted by subject, Phase, day, and time, noting treatment; summaries will be presented by treatment, gender and overall.

Unless stated otherwise, descriptive summaries will include n, mean, standard deviation (SD), coefficient of variation (%CV), median, minimum, and maximum for safety and PK parameters, geometric mean with associated 95% confidence interval (CI), and the between-subject CV (%CVb) for selected PK parameters, whereas n and percent will be used as summary statistics for categorical safety variables.

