2. SUMMARY OF KEY PROTOCOL INFORMATION

2.1. Changes to the Protocol Defined Statistical Analysis Plan

There were no changes or deviations to the originally planned statistical analysis specified in the protocol dated 04-MAY-2015, protocol amendment 1 dated 10-NOV-2015, protocol amendment 2 dated 30-MAR-2016 and protocol amendment 3 dated 14-AUG-2017.

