5.3. Reporting Conventions

- Statistical data analyses will be performed by, or under the direct auspices of, Clinical Statistics and Programming, GlaxoSmithKline.
- Data will be listed and summarized according to GlaxoSmithKline reporting standards, where applicable. Listings will be sorted by Site, subject, phase, day, and time, noting treatment; summaries will be presented by treatment (for safety and study population) or sex (for PK data), or by Site (demog), day, and time.

- Unless stated otherwise, descriptive summaries will include n, mean, standard deviation (SD), coefficient of variation (%CV), median, minimum, and maximum, geometric mean with associated 95% confidence interval (CI), and the between-subject CV (%CVb) for continuous variables, whereas n and percent will be used as summary statistics for categorical variables.
- Baseline or pre-dose assessment is the last available assessment prior to time of dose administration unless it is specified otherwise. If there are multiple assessments collected on the same scheduled time, the average of these assessments will be used. For tabulated safety summaries, only the scheduled assessments will be included in the summary tables. Unscheduled assessments will be presented in listings.
- Deviations from planned times will be examined for scheduled assessments. PK parameters will be calculated using actual assessment times. Actual assessment times will be used in the individual concentration-time plots. Nominal times will be used for the purposes of summarization and in mean and median plots. Concentration-time data will be listed using actual assessment times.
- Any changes/deviations to the analyses specified in the RAP will be described in the final Clinical Pharmacology Study Report (CPSR).
- Version 9.4 or higher of the SAS system will be used to analyze the CRF data as well as to generate tables, figures, and listings. PK parameters will be calculated using standard non-compartmental methods using Phoenix WinNonLin Version 7 or higher.
- All final displays will be produced according to Clinical Data Interchange Standards Consortium (CDISC) reporting standards based on the final Study Data Tabulation Model (SDTM) and Analysis Data Model (ADaM) datasets.

Data Type	Source	Format of Data	Planned Date of Final File	Responsibility
Safety	Database	SDTM	DBF	Data Management
	SMS2000 /PK HARP	DAT	Prior to SDL	DMPK

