7.2. Adverse Events

Adverse event verbatim text will be coded and classified by system organ class (body system) and preferred term using a standardized GSK coding system: Medical Dictionary for Regulatory Activities (MedDRA, v22 or higher). Treatment emergent AEs data and drug-related AEs for lead-in phase and for LA dosing phase will be summarized by Site and treatment and overall. The relationship of AE system organ class, preferred term, and verbatim text will be listed. All AEs will be listed by Site, subject and treatment. Serious adverse events (SAEs) will be listed. A listing of grade 3 or 4 non-ISR AEs will be provided if any grade 3 or 4 AE occur.

Injection site reaction (ISR) symptoms, size, severity grade and duration for the LA dosing phase will be summarized overall and will be listed by Site and subject.

For subjects who have an ISR that is serious, Grade 2 if persistent beyond 2 weeks, any Grade 3 or if any ISR persistent beyond 30 days and others if the Investigator or Medical Monitor feels it is medically necessary, a listing will be provided in table listing. All ISR data including treatment received and medical intervention as well as reaction outcome will be listed by subject. Plots of top 3 injection site reaction duration will be provided.

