11.1.2. Safety

Figures

Figure No. 2.X	Population	IDSL No. / Example Shell	Title	Additional Programming Notes	QC Level	Deliverable Priority
1	Safety	LAI116815, Figure 2.3	Individual Subject ISR Duration for the Top 3 ISRs	Select the top 3 ISRs, like Pain, nodule, and induration	1	SAC

Tables

Table No.	Population	IDSL No. / Example Shell	Title	Programming Notes	QC Level	Deliverable Priority
2.1	Safety	LAI116815/Table 2.1	Summary of Exposure Data	Include number of dose(s), formulation/route, and injection site, needle length, fat depth, injection length, etc Sorted by Site	1	SAC
2.2	Safety	IDSL, AE2	Relationship of Adverse Event System Organ Classes, Preferred Terms, and Verbatim Text		2	SAC
2.3	Safety	IDSL, CP_AE1x	Summary of All Adverse Events	By Site and Overall	2	SAC
2.4	Safety	IDSL, CP_AE1x	Summary of Drug-Related Adverse Events	Include all study treatment related, not procedure related AEs By Site and Overall	2	SAC

Table No.	Population	IDSL No. / Example Shell	Title	Programming Notes	QC Level	Deliverable Priority
2.5	Safety	IDSL, CP_AE9a	Listing of Subjects with Serious Adverse Events		1	SAC
2.6	Safety	IDSL, CP_AE9	Listing of Adverse Events Leading to Permanent Discontinuation of Study Drug or Withdrawal from Study		1	SAC
2.7	Safety	LAI116815, Table 2.7	Listing of Grade 3 and 4 Adverse Events		1	SAC
2.8	Safety	LAI116815, Table 2.8	Summary of Injection Site Reaction by Site and Overall	This table summarizes the data at Subject level; 'LM CAB 600mg SD' only, by site and overall	2	SAC
2.9	Safety	LAI116815, Table 2.9	Summary of ISR Event by Toxicity Grade for Each Site and Overall	This table summarizes the data at event level for 'IM CAB 600mg SD' only; by site and overall	2	SAC
2.10	Safety	LAI116815, Table 2.10	Summary of Injection Site Reaction Symptoms Maximum Size Measured in Diameter(cm) by Site and Overall	Average the max of each event size for each subject with ISR by treatment; 'IM CAB 600mg SD' only	2	SAC
2.11	Safety	LAI116815, Table 2.11	Summary of Duration of Injection Site Reaction by Site and Overall	This table summarizes the data at ISR event level; IM CAB 600mg SD' only	2	SAC
2.12	Safety	LAI116815, Table 2.12	Listing of Grade 2 or Higher Injection Site Reaction Symptoms or ISR persist beyond 30 days	For ISR	2	SAC
2.13	Safety	LAI116815, Table 2.13 IDSL, LB13	Listing of Reference Ranges for Clinical Laboratory Tests		1	SAC

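### The SAP drops the by-sex safety summaries that Protocol 9.4 calls for without declaring it, so events from women-only biopsies are summarised over a denominator of both sexes

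*SAP*

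**What the plan says.** Protocol 9.4, in its general paragraph on listings and summaries, states that "summaries will be presented by treatment, gender and overall". The next paragraph of that section specifies the descriptive statistics, among them "median, minimum, and maximum for safety and PK parameters", and counts and percentages for categorical safety variables.

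SAP 5.3 carries the corresponding sentence in altered form: "summaries will be presented by treatment (for safety and study population) or sex (for PK data"), with site mentioned for demography. SAP 7.2 then says: "Treatment emergent AEs data and drug-related AEs for lead-in phase and for LA dosing phase will be summarized by Site and treatment and overall". In SAP 11.1.2, Tables 2.3 and 2.4 (all and drug-related adverse events), Tables 2.8 to 2.11 (injection site reactions) and Table 2.18 (laboratory abnormalities of Grade 2 or higher) are specified by site and overall. None of the safety tables is specified by sex, whereas many PK displays in SAP 11.1.3 are.

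The programming note for Table 2.4 reads "Include all study treatment related, not procedure related AEs". No other table summarises procedure-related events.

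SAP 2.1 states: "There were no changes or deviations to the originally planned statistical analysis specified in the protocol".

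**The concern.** There are two linked problems. The first is a departure from the protocol that the SAP does not acknowledge: sex has been removed as a stratum for safety and site used in its place, while SAP 2.1 says that nothing changed.

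The second is what the removal does in this trial, where sex determines which invasive procedures a subject undergoes. Cervical biopsies are taken only from women, at Day 29 of the lead-in and at five visits after the injection. Vaginal biopsies are taken only from women, at Day 29 and then at Day 3 and Week 8 after the injection. Men have rectal sampling; women have it only if they consent. Protocol 4.6.1 names the risks of the genital biopsies: "There is also a small risk of bleeding and an extremely low risk of infection after biopsy". With procedure-related events kept out of Table 2.4 and no summary of their own, they reach a summary only through Table 2.3, where the percentage is taken over men and women together. A reader of that percentage would see a women-only event at a rate well below the rate among the women who could have it.

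**Working it through.** **Side-by-side reading.** Protocol 9.4 gives the strata as treatment, gender and overall, without limiting them to PK, and goes straight on to safety variables. SAP 5.3 covers the same ground, assigns treatment to safety and study population, and reserves sex for PK. The SAP sentence addresses safety in the very place where the protocol's rule stood, which supports reading the protocol rule as covering safety too.

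**Inputs.**
- Planned evaluable subjects: 8 men and 8 women, 16 in all, from about 20 enrolled (Protocol 9.2.1). The check 8 + 8 = 16 reproduces the plan's figure; the male share is 8/16 = 50%.
- Safety Population: everyone with at least one dose, both sexes (SAP 4). Its sex split is not stated.
- Women-only procedures: cervical and vaginal biopsy (Protocol 4.4, Table 4; Protocol 7.5).

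**Dilution of a women-only event.** Let x women have the event, W be the number of women and N the table denominator. The table shows x/N, the rate among women is x/W, and the displayed rate is W/N of the rate among women.
- 8 women of 16: 8/16 = 0.50.
- 20 dosed, with 8, 10 or 12 women (assumed range): 8/20 = 0.40, 10/20 = 0.50, 12/20 = 0.60.

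**Illustration with 2 affected women (event count assumed; exact Clopper-Pearson 95% intervals).**

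| Denominator | Rate | 95% CI |
|---|---|---|
| 8 women | 2/8 = 25.0% | 3.2 to 65.1% |
| 16, both sexes | 2/16 = 12.5% | 1.6 to 38.3% |
| 10 women | 2/10 = 20.0% | 2.5 to 55.6% |
| 20, both sexes | 2/20 = 10.0% | 1.2 to 31.7% |

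**Illustration with no events.** The one-sided 95% upper bound is 1 − 0.05^(1/n): 31.2% for n = 8 and 17.1% for n = 16; 25.9% for n = 10 and 13.9% for n = 20. The pooled denominator makes the absence of events look more reassuring than it is.

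**Rectal sampling.** If all 8 men and k of the 8 women are sampled, the displayed rate is (8 + k)/16 of the rate among those sampled: 8/16 = 0.50 at k = 0, 12/16 = 0.75 at k = 4, and 16/16 = 1.00 at k = 8. No planned safety table gives k.

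**Cell size.** If there are two sites, a site column averages 16/2 = 8 subjects, the same as a sex column. Small cells therefore do not explain choosing site over sex.

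**The case against.** The best case for the SAP is that this is a matter of layout in descriptive secondary tables. The protocol's promise is one general sentence; Protocol 9.4.2, which deals with safety specifically, refers only to the sponsor's reporting standards and does not mention sex, and the synopsis promises gender splits only for PK parameters. The safety objective concerns the drug, and nowhere do the documents promise an incidence for biopsy harms. All adverse events are listed by subject, sex is a listed demographic, and serious, Grade 3-4 and withdrawal-related events have their own listings. With 16 to 20 subjects a reader can count the affected women and divide by the number of women.

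Much of this stands. It limits the size of the point, and it means that a procedure-specific table is an addition to the protocol's promise. It does not remove the mismatch: 9.4.2 does not withdraw the rule in 9.4, and SAP 2.1 still denies any change.

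Three stronger readings are tempting but unsupported.
- A reader might infer that the all-event rate under the injection is wrong because it contains biopsy events. A table of all adverse events properly includes them whatever the cause, and Table 2.4 already separates drug-related events.
- A reader might infer from Protocol 4.5, which predicts that "males will achieve a higher C"max than females, that pooling hides a sex difference in drug reactions. The prediction is from a PK model, and the documents do not link Cmax to adverse events or injection site reactions.
- A reader might infer that every women-only rate is exactly halved. That requires 8 women in a denominator of 16, and the split of the Safety Population is not fixed.

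**Conclusion.** The point holds as an undeclared inconsistency between protocol and SAP that distorts one kind of displayed rate. Women-only procedural events would be shown at 0.5 of the rate among women with 8 women of 16, and at 0.4 to 0.6 of it under the assumed 8 to 12 women of 20. Rectal procedure events would be diluted by an amount that depends on how many women consent. Because the by-subject listings allow the rates to be rebuilt, the defect lies in the summaries and not in the data. No primary endpoint or inferential result is affected, and the matter is one of reporting, with no bearing on clinical management. It is worth correcting because safety and tolerability is a stated secondary objective and the correction is cheap.

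**What to change.** In SAP 5.3 and 7.2, restore the protocol's rule and present Tables 2.3, 2.4, 2.8-2.11 and 2.18 by treatment (where more than one applies), sex and overall. The by-site versions may stay alongside.

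Add one descriptive summary of procedure-related adverse events, by procedure (cervical or vaginal biopsy; sigmoidoscopy or rectal sampling), with the subjects who had that procedure as the denominator. A sex column alone would not fully serve, since a woman withdrawn before Day 29 is in the Safety Population without having been biopsied, and only some women may have rectal sampling.

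If any safety summary is still not given by sex, say so in SAP 2.1 with the reason.

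The cost is wording, extra columns and one extra table, from data already collected. The drawback is small cells, about 8 per sex, so the results should be read descriptively only.

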5.4.1. Liver Chemistry Stopping Criteria

For subjects with ALT elevation $\geq 1.25x$ but $< 3xULN$, retest ALT within one week. If the retest ALT is $< 1.25x ULN$, subjects may continue to Day 28 dosing. If the retest ALT is $\geq 1.25x ULN$, dosing will be terminated, and subjects are prohibited from entering the injection phase. Weekly assessments should be conducted until ALT is $< 1.25x ULN$. For subjects with ALT elevation $\geq 1.25x ULN$ at Day 29, dosing will be terminated, subjects are prohibited from entering the injection phase, and weekly assessments should be conducted until ALT is $< 1.25x ULN$. Subjects with ALT $\geq 3xULN$ at any time point will be discontinued from study treatment. Please refer to the Liver Safety Required Actions and Follow up Assessments Section in [Appendix 2](#) for subsequent evaluations. If any of the above develops, please notify the medical monitor.

[figure not shown]
Standard liver chemistry stopping and increased monitoring criteria have been designed to assure subject safety and evaluate liver event etiology (in alignment with the

FDA premarketing clinical liver safety guidance).

<http://www.fda.gov/downloads/Drugs/GuidanceComplianceRegulatoryInformation/Guidances/UCM174090.pdf>

Study treatment will be discontinued **for a subject** if liver chemistry stopping criteria are met prior to CAB LA injection. If liver stopping criteria are met after receiving a CAB LA injection, subjects will not be withdrawn from the study but continue to have safety assessments performed as noted below and within the Time and Events table for 52 weeks post-injection or until resolution of the liver event, whichever is longer.

Liver Chemistry Stopping Criteria – Liver Stopping Event Algorithm

Liver Safety Required Actions and Follow up Assessments Section can be found in [Appendix 2](#).

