
NOTES:
 
 1. An overnight fast is preferred prior to screening laboratory assessments; however, a minimum of a 6 hour fast is acceptable. 2. Details of Liver Chemistry Stopping Criteria and Required Actions and Follow-Up Assessments after liver stopping or monitoring event are given in Section 5.4.1 and Appendix 2. 3. STD screening tests will be performed per local site standards. Preferably, urine should be sent for nucleic acid testing (NAAT) for gonorrhea (GC), Chlamydia and trichomonas, and a rectal swab should be sent for NAAT for GC and Chlamydia. For syphilis screening, a plasma RPR will suffice. 4. Local urine testing will be standard for the protocol unless serum testing is required by local regulation or ethics committee or site preference. 				

All laboratory tests with values that are considered clinically significantly abnormal during participation in the study or within 52 weeks after the last dose of study treatment

should be repeated until the values return to normal or baseline. If such values do not return to normal within a period judged reasonable by the investigator, the etiology should be identified and the sponsor notified.

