5.2. Baseline Definition

For all endpoints (except as noted in baseline definitions) the baseline value will be the latest pre-dose assessment with a non-missing value, including those from unscheduled visits. If time is not collected, Day 1 assessments are assumed to be taken prior to first dose and used as baseline. If there are multiple assessments collected on the same scheduled time, the average of these assessments will be used.

The following table indicates the baseline day to be used in the analysis for each phase of the study:

Parameter	Baseline (Pr	edose) Days Collected	Baseline (Predose) Day Used in Analysis
	Screening	Day 1 of Each Phase	
Laboratory	Х	X*	Screening (or Day 1 predose in the lead-in phase if collected) for the lead-in phase; Day 1 predose for the injection phase
Vital Signs	Х	Х	Day 1 (Predose) for each phase
ECG	Х	Х	Screening (or Day 1 predose in the lead-in phase if collected) for all subjects

* The results of the hematology with differential, and clinical chemistry tests on Day 1 are not required prior to administering the first oral dose of CAB 30 mg, but should be drawn prior to CAB administration.

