5.6.3. Multiple Measurements at One Timepoint

Where multiple measurements are recorded for a particular time point, the mean of the measurements will be calculated and used in any derivation of summary statistics. However, all available data will be listed.

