5.7. Assessment Windows

Scheduled visits and unscheduled visits for lab, ECG and vital sign data will be assigned to assessment windows by actual study day. For PK, tissues and fluid samples, actual days will be used to calculate the actual visit Week (round-up), and evaluable samples will be summarized by actual visit week. Actual days will be used for the listings, and scheduled windows will be used for the Summary Displays.

Phase	Study Visit and Unscheduled Visit window	Reported on Summary Displays
Screen	30 days prior to Day 1	Screen
Oral Lead-in	Day 1, Day 14, Day 29	Day 1, Day 14, Day 29
Injection phase	Days 1,3,5,8	Days 1,3,5,8
	Week 4 \pm 3 days	Week 4
	Week 8 ±3 days	Week 8
	Week 12 ±3 days	Week 12
	Week 24 ±3 days	Week 24
	Week 36 ±3 days	Week 36
	Week 52 ±3 days	Week 52

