2.14	Safety	LAI116815, Table 2.14	Summary of Hematology Data by Treatment and Time by Site and Overall	Include oral CAB 30mg and 600mg LA in one table	2	SAC
2.15	Safety	LAI116815, Table 2.15	Summary of Change from Baseline in Hematology Data by Treatment and Time by Site and Overall		2	SAC

Table No.	Population	IDSL No. / Example Shell	Title	Programming Notes	QC Level	Deliverable Priority
2.16	Safety	LAI116815, Table 2.16	Summary of Clinical Chemistry Data by Treatment and Time for Each Site and Overall		2	SAC
2.17	Safety	LAI116815, Table 2.17	Summary of Change from Baseline in Clinical Chemistry Data by Treatment and Time for Each Site and Overall		2	
2.18	Safety	LAI116815, Table 2.19	Summary of Treatment Emergent Grade 2 or Higher Lab Abnormalities for Each Site and Overall	Include all tests in which we have DAIDS criteria.	1	SAC
2.19	Safety	LAI116815, Table 2.20	Listing of Treatment Emergent Grade 2 or Higher Lab Abnormalities	Include all tests in which we have DAIDS criteria.	1	SAC
2.20	Safety	LAI116815, Table 2.21	Summary of Vital Signs by Treatment and Time	Include BP, HR, and Temperature	2	SAC
2.21	Safety	LAI116815, Table 2.22	Summary of Change from baseline in Vital Signs by Treatment and Time	Include BP, HR, and Temperature	2	SAC
2.22	Safety	LAI116815, Table 2.23	Listing of All Vital Signs for Subjects with Any Values of Potential Clinical Importance		1	SAC
2.23	Safety	LAI116815, Table 2.24	Summary of ECG Findings		2	SAC
2.24	Safety	LAI116815, Table 2.25	Summary of ECG Values		2	SAC
2.25	Safety	LAI116815, Table 2.26	Summary of Change from baseline for ECG Values		2	SAC
2.26	Safety	LAI116815, Table 2.27	Summary of Category of QTc Data by Treatment and Time		2	SAC
2.27	Safety	LAI116815, Table 2.28	Summary of Category of QTc Change from Baseline by Treatment and Time		2	SAC
2.28	Safety	IDSL, CP_EG6	Listing of Clinically Significant ECG Abnormalities	List all data for a subject with clinically significant abnormalities	1	SAC
2.29	Safety	IDSL, CP_EG4, LAI116815, Table 2.29	Listing of All ECG Values for Subjects with Any Value of Potential Clinical Importance		1	SAC

Table No.	Population	IDSL No. / Example Shell	Title	Programming Notes	QC Level	Deliverable Priority
2.30	Safety	IDSL, SP1	Listing of Surgical Procedures	See format	1	SAC
2.31	Safety	IDSL, MH2	Listing of Medical Conditions	See format	1	SAC

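### SAP 5.3 and 5.7 conflict on unscheduled laboratory results, and Table 2.18 has no worst-grade rule, so the Grade 2+ laboratory count can miss or under-grade a subject

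*SAP*

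**What the plan says.** **SAP rules.**

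- Section 5.3: "For tabulated safety summaries, only the scheduled assessments will be included in the summary tables. Unscheduled assessments will be presented in listings".
- Section 5.7: "Scheduled visits and unscheduled visits for lab, ECG and vital sign data will be assigned to assessment windows by actual study day", and "scheduled windows will be used for the Summary Displays". Its window table gives lead-in Days 1, 14 and 29 as single days. Weeks 4, 8, 12, 24, 36 and 52 carry ±3 days.
- Section 5.6.3, for several measurements at one time point: "the mean of the measurements will be calculated and used in any derivation of summary statistics". All data are still listed.
- Section 5.2 lets the latest pre-dose value serve as baseline, "including those from unscheduled visits".
- Section 7.5 derives toxicity grades in the analysis dataset, without saying whether before or after any averaging, and lists Grades 2 to 4 with actual date and time.
- Section 11.1.2, Table 2.18: "Summary of Treatment Emergent Grade 2 or Higher Lab Abnormalities for Each Site and Overall". The programming note says which tests to include, not which value per subject is graded. Table 2.19 is the matching listing.

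**Protocol sampling.**

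- Section 5.4.1, for ALT from 1.25x to below 3x ULN: "retest ALT within one week", with weekly checks if it stays raised.
- Appendix 2: after a liver stopping event, repeats within 24 hours or 24 to 72 hours, then twice weekly or weekly.
- Section 7.4.6: clinically significant abnormal results "should be repeated until the values return to normal or baseline", up to 52 weeks after the last dose.
- Section 7.1.2: after injection, chemistry and haematology are marked at Weeks 4, 8 and 12 and at withdrawal, but not at Weeks 24, 36 or 52.

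**The concern.** Table 2.18 is a tabulated safety summary, so 5.3 applies to it. The protocol relies on off-schedule samples to confirm and follow laboratory toxicity once a first value is abnormal, and for a subject who completes the study those are the only possible chemistry results after Week 12. If such a sample holds the subject's worst value, 5.3 keeps it out of the table meant to count it. Section 5.7 points the other way, so a programmer cannot follow both, and nothing visible in the SAP settles which governs.

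Safety is a secondary objective, and raised transaminases are the first risk in the protocol's risk table. What is at stake is a descriptive count: Tables 2.18 and 2.19 cover the same abnormalities yet could show different subjects or different maximum grades.

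**Working it through.** The plan gives no figure to reproduce, so the check applies each rule in turn. Two assumptions: conditional retests count as unscheduled (the SAP does not define the term), and a value in no window does not reach the summary displays. All ALT values are illustrative.

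**Step 1. Grade bands (Protocol Appendix 4, ALT).** Grade 1 is 1.25 to <2.5x ULN, Grade 2 is 2.5 to <5x, Grade 3 is 5 to <10x, Grade 4 is 10x or more.

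**Step 2. Which retests fall in a 5.7 window?** Week w is taken as Day 7w, with the scheduled visit on its nominal day.

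- Retest within a week of Day 14: Days 15 to 21. The only lead-in windows are Days 1, 14 and 29, so 0 of 7 days qualify.
- Weekly checks after Day 29: Days 36, 43 and 50. None qualifies.
- Retest 1 to 7 days after Week 4: Days 29 to 35. The window is Days 25 to 31, so 3 of 7 days qualify. Weeks 8 and 12 behave the same way.
- Repeat 1 to 3 days after Week 4, 8 or 12: 3 of 3 days qualify.
- After Week 12 (Days 85 to 364, 280 days): 3 days in the Week 12 window plus 7 + 7 + 4 = 18 in the Week 24, 36 and 52 windows, 21 in all. 21/280 = 7.5%, so 259 days lie outside every window.

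**Step 3. Grade shown under each rule.** Scheduled value first, retest second, in multiples of ULN.

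| Pair | 5.3: scheduled only | Mean (5.7 with 5.6.3, if applied to grading) | Worst single value |
|---|---|---|---|
| 2.0 / 2.8 | Grade 1 | (2.0 + 2.8)/2 = 2.4, Grade 1 | Grade 2 |
| 3.2 / 5.5 | Grade 2 | (3.2 + 5.5)/2 = 4.35, Grade 2 | Grade 3 |
| 2.6 / 2.0 | Grade 2 | (2.6 + 2.0)/2 = 2.3, Grade 1 | Grade 2 |
| 3.5 / 8.0 | Grade 2 | (3.5 + 8.0)/2 = 5.75, Grade 3 | Grade 3 |

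The mean column can arise only for retests inside a Week 4, 8 or 12 window. It lowers the grade in the first three pairs and not in the fourth.

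**Step 4. The lead-in case.** Let the first pair be a Day 14 value and its retest on Days 15 to 21, with no scheduled value reaching 2.5x ULN. Under 5.3 the retest is unscheduled and excluded. Under 5.7 it has no window. Table 2.18 omits the subject on both readings, although under Protocol 5.4.1 that retest ends dosing and bars the injection.

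**Step 5. Size.** The Safety Population is everyone with at least one dose, about 20 subjects. 1/20 = 5 percentage points. For a subject who completes the study, the period without scheduled chemistry is 52 − 12 = 40 weeks.

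**The case against.** The best defence is that nothing is hidden from the report. Section 5.3 itself sends unscheduled results to listings, Table 2.19 and Section 7.5 list the graded abnormalities, and Section 7.5 separately lists laboratory abnormalities recorded as adverse events. Clinically significant values are adverse events under Protocol Appendix 3, and liver stopping events have their own case report form and 24-hour reporting. The study is small and its safety analysis is descriptive. Table 2.18 also follows a shell from another study that is not in these documents, and a counting rule may sit there. All of this stands. It limits the harm to one summary count but does not settle which SAP rule governs that count.

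A reader might infer more than the documents support:

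- *That unscheduled results are both excluded and averaged.* These are alternative readings; one result cannot be both.
- *That averaging will lower grades.* Section 5.6.3 speaks of summary statistics, not of toxicity grades, and it could reach only retests in the Week 4, 8 and 12 windows.
- *That all chemistry after Week 12 is lost.* Withdrawal-visit chemistry is scheduled and can fall after Week 12. Under 5.7, a single unscheduled value in a Week 24, 36 or 52 window has no scheduled value to be averaged with.
- *That a liver stopping event on a scheduled sample drops out.* Under 5.3, a scheduled ALT of 3x ULN or more is at least Grade 2 and is counted.
- *That every safety table excludes unscheduled values.* Section 5.2 admits them as baselines.
- *That the QTc category tables need a new row.* The problem shown here concerns laboratory data.

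**Conclusion.** The point holds in limited form. Sections 5.3 and 5.7 conflict, and Table 2.18 has no visible worst-grade rule. Under 5.3 as written, the table can omit a subject whose only Grade 2+ value came from an off-schedule sample, or understate a maximum grade. For ALT retests on Days 15 to 21 of the lead-in, it can do so under either section. Lowering by averaging is a further possibility only if 5.7 is followed and the 5.6.3 mean is carried into grading.

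Each affected subject moves the count by about 5 percentage points of roughly 20. The documents do not show how many subjects would be affected. The conclusion rests on the two assumptions stated in the working and on the unseen table shell not supplying the missing rule.

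**What to change.** Four changes to the SAP:

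1. **5.3:** limit the scheduled-only sentence to the by-visit summary and change-from-baseline tables (2.14 to 2.17, 2.20 to 2.21, 2.24 to 2.25). Word it so that the handling of the other ECG tables does not change.
2. **Table 2.18:** derive it from each subject's worst single post-baseline value per phase, scheduled or unscheduled, through Week 52. State which phase holds washout samples.
3. **5.6.3:** state that averaging does not apply to laboratory toxicity grading.
4. **5.7:** make it agree with 5.3, so that unscheduled laboratory values do not enter the by-visit summaries and the Table 2.18 count does not depend on windows.

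The cost is SAP wording and minor programming. Counts in Table 2.18 may be slightly less favourable. No sampling or clinical rule changes.
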